## FATHERHOOD FIRE EVALUATION PLAN

### GLOSSARY OF TERMS

There are different types of program evaluations and many different ways to describe them. To facilitate communication, the terms used here are described below:

- **Implementation Evaluation:** An evaluation that addresses the extent to which a program is operating as intended. It describes who participated in the program, the services they received, and how services were provided. It assesses program operations and whether the population targeted was served. Implementation evaluation helps identify why a program's intended outcomes were or were not achieved. Implementation evaluation cannot address whether changes have occurred as a result of the program. It is also called a process evaluation or formative evaluation.
- **Outcome Evaluation:** Outcome evaluation is used to measure the results of a program. It assesses whether the program led to intended changes in participants' knowledge, skills, attitudes, behaviors, or awareness. It can be descriptive or impact depending on whether it seeks to address whether the intended changes were the result of the program.
- **Impact Evaluation:** Impact evaluation is a type of outcome evaluation that attributes participant changes to the program. To do so, it includes a comparison or control group to help establish that program activities, not something else, caused the changes in the observed outcomes. In this design, two groups are included in the evaluation: (1) a treatment group that includes individuals who participate in the program; and (2) a comparison group that includes individuals who are similar to those in the treatment group, but who do not receive the same services.
- **Descriptive Evaluation:** Descriptive evaluation is a type of outcome evaluation that measures change in outcomes by making comparisons among participants after

program participation and conditions prior to participation. This design involves collecting information only on individuals participating in the program. This information is collected at least twice: once before participants begin the program and sometime after they complete program.

## PROGRAM BACKGROUND

### 1. PROGRAM SUMMARY

*Please provide a brief summary of your grant project including the needs to be addressed, the services provided, and the population served.*

The purpose of this project is to help fathers establish and strengthen their relationship with their children and the mothers of their children; to reduce domestic violence in vulnerable families; to improve economic stability of fathers through comprehensive, job-driven career services; to employ intensive case management barrier removal, individual job coaching, and comprehensive family development to improve short and long-term outcomes.

The target population for this project are low-income urban father in high poverty and high-risk neighborhoods who are above the age of 18 with children under the age of 24. These fathers include non-custodial and custodial fathers, TANF eligible fathers, fathers at or below federal poverty levels, and fathers with children in early childhood learning centers. This project also focuses on fathers who have been or may be at risk of domestic violence (victims and perpetrators), under-involved or unininvolved in their children's lives, unemployed, underemployed, lacking in education (GED/diploma), in need of job skills, or experiencing the following barriers: criminal records, mental health conditions, addictions, or disabilities.

This project is needed in this community because Franklin County is the most populous county in Ohio with 1.3 million residents and a poverty rate of 16.7%. The largest city in Franklin County, Columbus, has a poverty rate of 20.2% for all residents but 31.4% among black residents and 32.1% among Hispanic residents. Furthermore, in the seven Columbus zip codes targeted in this project, the average poverty rate is 45.1%. The Columbus Metro region is one of the most racially and economically segregated regions in the country.

This persistent and pervasive poverty negatively impacts upward mobility of families, exacerbates disparities, and reinforces generational poverty. Additionally, in Ohio, 1 in 3 women and 1 in 4 men have experienced some form of physical violence by an intimate partner which accounts for 15% of all violent crime. Since March 2020 there has been a 20% increase in domestic violence calls due to COVID-19 shutdowns and US Labor Department data shows the national unemployment rate among blacks has tripled. Funds from this grant will be used to address, support, and integrate all three authorized activities: Responsible Fatherhood, Healthy Marriage and Relationships, and Economic Stability.

All In Dads! will take an integrated and comprehensive approach utilizing parenting education, intensive case management, coaching, mentoring, and employment services to improve long-term outcomes for our target population. All In Dads! will educate fathers and couples to improve the quality of and increase the frequency of father/child engagement, improve spousal/co-parent-parenting pair relationships, reduce conflict and domestic violence, and create safer and happier families by improving child and parent well-being, self-esteem, and health.

## 2. EVALUATION GOALS

*Please briefly describe key goals of your evaluation and what you hope to learn below.*

The goals for the AFC Fatherhood project are improved family functioning (parenting and co-parenting), improved adult and child well-being, increased economic stability and mobility, and reduced poverty by providing intensive, integrated services in promoting responsible parenting and economic stability with funds from The Fatherhood Family-Focused Interconnected, Resilient and Essential Grants. Evaluation goals include achieving sufficient sample size, retaining participants through the use of incentives, collecting valid and complete data, and ultimately making a contribution to the field of responsible fatherhood in the literature.

## 3. EVALUATION ENROLLMENT

*Please provide the expected start and end dates for program and evaluation enrollment using the tables below. For impact studies, please indicate expected start and end dates for each study group.*

DESCRIPTIVE EVALUATION		
Please leave blank if not conducting a descriptive outcome evaluation.		
	Program Enrollment	Study Enrollment
Start Date	4/1/2021	4/1/2021
End Date	9/30/2025	3/31/2024
Definition	All participants enrolled for services	All participants enrolled for services to include local evaluation

#### 4. EVALUATION TIMELINE

*Please include a timeline for key activities of the evaluation below. Example of activities may include IRB submission, staff training, waves of data collection, analysis period, and report writing and submission.*

Evaluation Activity	Start Date	End Date
Additional Evaluation staff hiring and onboarding	1/15/2021	2/15/2021
Evaluation staff training	1/22/2021	2/20/2021
Evaluation Kickoff meeting and orientation with all program staff	2/2/2021	2/3/2021
IRB training and certification by all program and evaluation staff	10/1/2020	2/28/2021
Development and submission of Evaluation Plan document	1/15/2021	2/19/2021
Evaluation Tools Development	10/1/2020	2/28/2021
IRB Approval	3/1/2021	3/15/2021
CQI Team Formed and Meeting bi-weekly	3/15/2021	7/1/2025
Training for CQI Team	3/15/2021	3/28/2021
Training for all Program Staff on Research Methods and process	3/15/2021	3/28/2021 + Refreshers as needed including new staff
Evaluation Data Collection	4/1/2021	5/31/2025
Baseline Data	4/1/2021	3/31/2024
Post Test Data	5/17/2021	8/2/2024
Follow-up Data	4/1/2022	5/31/2025 at the latest
1 st Manuscript submitted for publication	7/1/2025	12/31/2025

Final Descriptive Report Submitted

12/1/2025

3/31/2025

## EVALUATION PLAN

### 1. RESEARCH QUESTIONS

#### 1.1. OVERVIEW OF RESEARCH QUESTIONS

*Please state the research question(s) that the evaluation intends to answer and for each research question indicate the type: implementation or outcome.*

- *Implementation Questions: Identifying whether a program has been successful in attaining desired implementation goals (e.g., reaching intended target population, enrolling intended number of participants, delivering training and services in manner intended, etc.)*
- *Outcome Questions: Identifying whether program is associated with intended outcomes for participants (e.g., do participants' knowledge, attitudes, behaviors, or awareness change?)*

Research questions in this study are framed by a Descriptive Evaluation Design to assess whether outcomes improve for low-income fathers who participate in the All in Dads! (AID!) Project. Primary and secondary outcomes are assessed before and after participants complete core curricula—*Father Factor*, *The New Playbook*, and *Money Smart*—and *Job Readiness Coaching and Career Development* as employment support services (pre to post). Primary outcome measures will indicate whether behavior improved for healthy family relationships (parent, co-parent, and partner). Secondary outcome measures will indicate whether behavior improved for the attitudes and expectations that facilitate and reflect behavior for healthy family relationships and economic stability (financial, employment) (see Table 1 below).

No	Research Question	Implementation or Outcome?
R1	Will participants report significantly healthier parenting behavior one-year after completing primary educational services and employment support services?	Primary Outcome
R2	Will participants report significantly healthier co-parenting behavior one-year after completing primary educational services and employment support services?	Primary Outcome
R3	Will participants report significantly healthier financial behavior one-year after completing primary educational services and employment support services?	Secondary Outcome
R4	Will participants report significantly healthier parenting attitudes after completing primary educational services and employment support services?	Secondary Outcome

## 1.2. OUTCOME RESEARCH QUESTIONS

For each outcome research question listed above, whether a descriptive or impact design, summarize the inputs (e.g., program components, program supports, implementation features, etc.), target population (e.g., the population for which the effect will be estimated) and the outcomes (e.g., child well-being, father-child engagement, etc.) that will be examined to answer the research question(s). Comparisons for descriptive evaluations may reflect circumstances before the grant, pre-treatment, or pre-determined benchmark from other studies with similar interventions.

Research Question Number Should correspond to the number indicated in Table 1.1 above	Intervention Program component or set of activities that the evaluation will test or examine	Target Population Population for which the effect of the treatment will be estimated	Comparison What the intervention will be compared to (e.g., pre-intervention for descriptive designs)	Outcome Changes that are expected to occur as a result of the intervention	Confirmatory or Exploratory? Confirmatory: those upon which conclusions will be drawn Exploratory: those that may provide additional suggestive evidence
R1	Primary curricula ( Father Factor, The New Playbook, and Money Smart ); Employment Support ( Job Readiness Coaching, Career Development ); Continuous Quality Improvement (CQI) Process	Low-income fathers who are 18+ years with children up to 24 years who are residents of Franklin County in Ohio	Assessment of healthy parenting behavior at AID! Project enrollment.	Participants who complete primary and support services will report healthier parenting behavior one year after AID! enrollment.	Confirmatory
R2	Primary curricula ( Father Factor, The New Playbook, and Money Smart ); Employment Support ( Job Readiness Coaching, Career Development );	Low-income fathers who are 18+ years with children up to 24 years who are residents of Franklin County in Ohio	Assessment of healthy co-parenting behavior at AID! Project enrollment.	Participants who complete primary and support services will report healthier co-parenting behavior one year	Confirmatory

	Continuous Quality Improvement (CQI) Process			after AID! enrollment.	
R3	Primary curricula ( Father Factor, The New Playbook, and Money Smart ); Employment Support ( Job Readiness Coaching, Career Development ); Continuous Quality Improvement (CQI) Process	Low-income fathers who are 18+ years with children up to 24 years who are residents of Franklin County in Ohio	Assessment of healthy financial behavior at AID! Project enrollment.	Participants who complete primary and support services will report healthier financial behavior one year after AID! enrollment.	Confirmatory
R4	Primary curricula ( Father Factor, The New Playbook, and Money Smart ); Employment Support ( Job Readiness Coaching, Career Development ); Continuous Quality Improvement (CQI) Process	Low-income fathers who are 18+ years with children up to 24 years who are residents of Franklin County in Ohio	Assessment of healthy parenting attitudes immediately following program completion post-intervention.	Participants who complete primary and support services will report healthier parenting attitudes immediately following program completion..	Confirmatory

## 2. BACKGROUND

For each outcome research question listed in 1.1, whether descriptive or impact design, briefly summarize the previous literature or existing research that informs the stated research question and how the evaluation will expand the evidence base. Explain why the research questions are of specific interest to the program and/or community. Only a short summary paragraph

*description is needed below. Additional documentation, such as a literature review, may be appended to this document.*

Research Question	Existing Research	Contribution to the Evidence Base	Interest to the Program and/or Community
R1	Low-income fathers can lack the parenting skills to fulfill their familial obligations as a parent to promote healthy family relationships.	Determine the extent to which the delivery of AID! Project services enhance the parenting skills of low-income fathers.	Inform practitioners about whether AID! Project design promotes healthy family relationships by improving parent behavior .
R2	Low-income fathers can lack the co-parenting skills to fulfill their familial obligations as a parent to promote healthy family relationships.	Determine the extent to which the delivery of AID! Project services enhance the co-parenting skills of low-income fathers.	Inform practitioners about whether AID! Project design promotes healthy family relationships by improving co-parent behavior .
R3	Low-income fathers can lack the financial skills to fulfill their familial obligations as managers of household finances to promote economic stability.	Determine the extent to which the delivery of AID! Project services enhance the financial management skills of low-income fathers.	Inform practitioners about whether AID! Project design promotes economic stability by improving financial behavior .
R4	Low-income fathers can lack parenting attitudes to facilitate the skills necessary to engage in healthy parenting behavior.	Determine the extent to which the delivery of AID! Project services enhance the parenting attitudes of low-income fathers.	Inform practitioners about whether AID! Project design promotes healthy family relationship by improving parenting attitudes .

### 3. LOGIC MODEL

*Clearly demonstrate how the research question(s) (and the related implementation features and/or participant outcomes) link to the proposed logic model and the theory of change for the program. You may append a copy of your logic model to this document.*

Figure 1 in appendix A presents a logic model to specify a theory of change for delivering AID! services. Service delivery processes specified in the model are linked to the desired outcomes for healthy family relationships and economic stability. Model specification incorporates a Descriptive Study design to conceptualize service delivery to assess outcomes for the AID! Project by comparing primary and secondary participant outcomes before and after participants complete services.

Service delivery processes: Key aspects of service delivery processes in the theory of change—goals, inputs, activities, and outputs—articulate the experiences that are designed to solve specific problems for those who agree to participate in the AID! Project. As a result, three broad service delivery goals are identified to maximize AID! Project participation benefits as explained below:

- **Goal 1 - Deliver core curricula as primary services to AID! participants:** Candidates will understand that they receive *core curricula* to develop their skills to engage in healthy behaviors for parenting, co-parenting, partner relations, employment, and financial management but only after receiving an orientation about the AID! Project and giving project staff informed consent to participate in study activities. Then, *Father Factor*, *The Next Playbook*, and *Money Smart* curricula will be delivered to participants as specified in the logic model.
- **Goal 2 - Deliver employment support services to AID! participants:** Candidates will understand that they receive *employment support services* to develop their skills to engage in healthy behaviors for parenting, co-parenting, partner relations, employment, and financial management, but only after receiving an orientation about the AID! Project and giving project staff informed consent to participate in study activities. Then, Case Managers will help Job Coaches promote Job Readiness and help the Career Development Manager with job placement and post-employment success for participants.
- **Goal 3 - Conduct Continuous Quality Improvement (CQI) to ensure full implementation of primary and enhanced employment services to participants:** Reports prepared and presented to the CQI Team by evaluators in each of the 5 steps in the CQI Process will use a series of performance indicators to track key outputs over time to identify any AID! services delivered that might fall short of the intended amounts to be offered (i.e., fidelity standards) and received (i.e., dosage thresholds) by them. The CQI Team will then work with project staff to develop and implement performance interventions to address any outputs that need improvement to ensure the services offered to and received by participants meet the intended amounts by the end of each program year.

Desired Outcomes: Outcomes specified in the logic model theorize the primary and secondary outcomes that are desired for participants after they complete *AID!* services. Secondary outcomes are the improved attitudes and expectations that indicate and reflect participant engagement in healthy parenting, partner relations, employment, and financial behaviors. Primary outcomes are the healthier behaviors exhibited by participants for parent, co-parent, and partner relationships that ultimately define the participation benefits for the AID! Project. All outcomes specified in the logic model are theorized to be more positive for eligible low-income fathers after they complete *primary services* and *post-employment support services*.

#### 4. HYPOTHESES

*For each specified research question, state the hypothesized result(s) and briefly describe why these results are anticipated.*

Research Question	Hypothesized Result
R1	Participants will report healthier parenting behavior one-year after they complete primary services and employment support services in the AID! Project.
R2	Participants will report healthier co-parenting behavior one-year after they complete primary services and employment support services in the AID! Project.
R3	Participants will report healthier financial behavior one-year after they complete primary services and employment support services in the AID! Project.
R4	Participants will report healthier parenting attitudes immediately after they complete primary services and employment support services in the AID! Project.

\* you may add rows by hitting the tab button, or right click and select insert row below

## 5. RESEARCH DESIGN

For each research question, briefly describe why the research design proposed will answer each research question(s). State whether the proposed evaluation is a descriptive or impact evaluation and justify why the proposed research design is best suited to answer the research question(s).

Research Question	Design	Justification
R1	Pre to follow-up assessment will estimate the impact of AID! participation on healthy parenting behavior .	Healthy change reported by participants in their parenting behavior from pre to 1-year follow-up estimates the maximum amount of benefit that can be attributed to AID! services in the absence of a counterfactual.
R2	Pre to follow-up assessment will estimate the impact of AID! participation on healthy co-parenting behavior .	Healthy change reported by participants in their co-parenting behavior from pre to 1-year follow-up estimates the maximum amount of benefit that can be attributed to AID! services in the absence of a counterfactual.
R3	Pre to follow-up assessment will estimate the impact of AID! participation on healthy financial behavior .	Healthy change reported by participants in their financial behavior from pre to 1-year follow-up estimates the maximum amount of benefit that can be attributed to AID! services in the absence of a counterfactual.
R4	Pre to post assessment will estimate the impact of AID!	Healthy change reported by participants in their parenting attitudes from pre to post estimates the maximum amount of benefit that

participation on **healthy parenting attitudes**.

can be attributed to AID! services in the absence of a counterfactual.

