AFC and MER are planning on the publication and presentation of the findings of this research effort, both in a descriptive manner in the project's early years and regarding outcomes and impacts over time. MER will produce at least one manuscript for publication and make two professional presentations on the program and its findings. AFC and MER will use the most appropriate and robust analytical method possible in reporting results, including in the final report for the project to OFA, and to making the de-identified dataset available to the public after the conclusion of this project. In addition, we will make use of the HMRF network and conferences to share information with the field, and we will empower Action for Children to use evaluation findings in communications with other partners, funders, and their community.

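### Protocol Section 5 presents one-group change as program impact and as the maximum attributable benefit; the glossary rules out the first for this design, and the second needs an unstated assumption

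*Protocol*

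**What the plan says.** Protocol Section 5 has one row per research question. For R1 to R3 the Design column reads "Pre to follow-up assessment will estimate the impact of AID! participation on" the outcome in question. R4 (parenting attitudes) makes the same claim for the change from pre to post. In all four rows the Justification column adds that the change "estimates the maximum amount of benefit that can be attributed to AID! services in the absence of a counterfactual".

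Elsewhere the plan describes a study without a comparator:

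- Protocol Section 1.1: "Research questions in this study are framed by a Descriptive Evaluation Design".
- Protocol Section 8.1: every program participant is a study participant, so there is one group.
- SAP Section 1 (Analytic approach): the main goal is to assess change scores among participants. Paired t-tests are used, and the binary account items are reported as percentages.

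The protocol's glossary defines the terms: "Impact evaluation is a type of outcome evaluation that attributes participant changes to the program". The means that the glossary names for this kind of evaluation is a comparator: "it includes a comparison or control group to help establish that program activities, not something else, caused the changes in the observed outcomes". Of a descriptive evaluation it says: "This design involves collecting information only on individuals participating in the program".

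SAP Section 3 (Dissemination) plans publication and presentation "regarding outcomes and impacts over time". The Background table (Section 2 of the Evaluation Plan) gives the contribution of each question as finding out how far AID! services improve the skill or attitude concerned.

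**The concern.** Section 5 is where the plan says what its results will mean, and Section 1.2 labels all four questions confirmatory, that is, the ones from which conclusions will be drawn. As worded, an improvement could be reported as program impact, and its size as a ceiling on the benefit. Without a comparator neither statement can be supported. If fathers would have improved anyway, the change overstates what the program did. If they would otherwise have worsened, it understates it, and a reader told that the figure is a maximum would wrongly rule out a larger benefit.

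**Working it through.** There is no stated figure to reproduce, so the check has three parts.

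**1. Wording against the glossary.** The glossary makes a comparison or control group the means by which an impact evaluation attributes change. Sections 1.1 and 8.1 and SAP Section 1 show a one-group descriptive study. Section 5 nevertheless uses the language of impact and attribution in every row. This is a direct contradiction. The glossary does not mention upper bounds, so it has no bearing on the word *maximum*.

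**2. The claim to a maximum.** Score every outcome so that positive means healthier. Let τ be the program effect and b the change that would be seen without it (time trend, regression to the mean, children growing older, change in how the survey is taken, selective follow-up). Then

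E[observed change] = τ + b.

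The change equals the effect only if b = 0, and it is an upper bound only if b ≥ 0. Example with assumed values in SD of change:

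| τ | b | Expected change |
|---|---|---|
| 0.20 | −0.10 | 0.10 (half the effect) |
| 0.20 | −0.20 | 0.00 |
| 0.00 | +0.10 | 0.10 (no effect at all) |

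The documents do not fix the sign of b. The pandemic conditions described in the Program Summary could ease, which would favour improvement. Children may be up to 24 and the SAP takes the youngest as focal child, so contact could fall as children age. Entrance surveys are proctored by staff, while the one-year survey may be taken by phone. Only fathers with both surveys are analysed, and 70% are expected at one year.

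**3. Size of a false signal, for illustration.** Inputs: n = 483 and two-sided α = 0.05 (Protocol Section 8.2); drift d in SD of change (assumed); τ = 0. The standard error is 1/√483 = 0.0455. The rejection rate of the paired t-test, by the normal approximation, is

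Φ(d√483 − z) + Φ(−d√483 − z),

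with z = 1.960 unadjusted. SAP Section 1 plans to adjust p-values but names no method. As one assumption, Bonferroni over the five continuous outcomes in the SAP table gives α = 0.05/5 = 0.01 and z = 2.576.

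| Drift d | d√483 | Unadjusted | Bonferroni over five |
|---|---|---|---|
| 0.05 | 1.099 | 19.6% | 7.0% |
| 0.09 | 1.978 | 50.7% | 27.5% |
| 0.128 | 2.813 | 80.3% | 59.4% |

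The exact noncentral-t calculation agrees to within half a percentage point in every cell. The table applies to R1, R2 and R4. It does not apply to R3, whose binary items get no t-test.

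**The case against.** The best defence is that the plan hides nothing. It calls the study descriptive in several places, the disputed sentence itself admits that there is no counterfactual, and the SAP states its aim as assessing change scores. That stands as mitigation: the SAP's analysis is descriptive, and nothing is wrong with the t-test as a test of change. It does not rescue Section 5, because that sentence concedes the missing comparator and still keeps the attribution.

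Three stronger readings are tempting and are not supported:

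- *The glossary also contradicts the word maximum.* It does not; that claim fails only by the reasoning in step 2.
- *Every confirmatory question will end in a significant t-test reported as attributable benefit.* R3's binary items are only described, and the SAP's analysis section nowhere says that a significant result will be attributed to AID!. The nearest support is one phrase in the dissemination paragraph.
- *The rejection rates show how far this study is biased.* They are points on the ordinary power curve. No document gives a drift size, and adjustment lowers the rates.

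It is also fair to say that recovery after the pandemic and regression to the mean from a low point would usually raise the change, which fits an upper-bound reading. But the plan states no such assumption, and other influences could run the other way.

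**Conclusion.** The point holds as a fault in the stated inference. In all four rows Section 5 claims impact and attribution that the protocol's glossary denies to a one-group design. The further claim to a maximum depends on non-program change being zero or favourable, which is neither stated nor testable here. This conclusion needs no numerical assumption.

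The size is illustrative only. It rests on assumed drift, n = 483 and zero program effect, and covers only the outcomes tested by paired t-test. Drift of 0.05 to 0.128 SD of change would give p < 0.05 in about 20% to 80% of studies unadjusted, or about 7% to 59% if Bonferroni over five outcomes is assumed. A reader might infer that the data collection or the tests are invalid; the documents do not support that. What needs correcting is what the results are said to show.

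**What to change.** - **Protocol Section 5, all four rows.** Replace the statement that the assessment will estimate impact with one that it will describe change among participants who completed both surveys (entrance and follow-up for R1 to R3, entrance and exit for R4). Delete the clause on the maximum attributable benefit. Add that the change may be larger or smaller than the program effect and will not be attributed to AID!.
- **Protocol Section 2 (Background), contribution column.** Reword the causal statements on how far services improve skills and attitudes so that they match; otherwise the inconsistency survives.
- **SAP Section 3.** In the phrase "regarding outcomes and impacts over time", keep outcomes and remove impacts.

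Data collection, sample and tests do not change. The only cost is a more modest claim.
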